7.2 Participant Withdrawal from the Study

Participants are free to withdraw from participation in the study at any time upon request. Upon withdrawal, all study interventions will cease.

7.3 Lost to Follow-Up

Loss to follow-up will be documented in the study registry.

8 - Study Assessments and Procedures

8.1 Efficacy Assessments

Screening

Subjects will be evaluated for entry into the study according to stated inclusion and exclusion criteria. Individuals who are identified during screening as not eligible for the study need not complete all screening procedures. The reason for ineligible status will be documented on the Screen Failure Log.

The following information will be obtained to evaluate each subject's qualifications for participation in the study:

From electronic health record (EHR):

- Demographic information including gender, date of birth, race, ethnicity
- Medical and medication history over the past 30 days
- Documentation of blood for standard of care (SOC) hematology, coagulation, clinical chemistry (if available)

- Physical examination including height and weight (body mass index will be calculated based on these variables), and vital signs (systolic and diastolic blood pressure, pulse rate, respiratory rate, pulse oximetry, body temperature), respiratory exam (crackles yes/no, wheezing yes/no, increased work of breathing yes/no), abdominal exam (abdominal tenderness yes/no) neurological exam (Glasgow Coma Scale)
- 12-lead electrocardiogram (EKG), Chest imaging findings (Chest X-Ray with infiltrates yes/no; ground-glass opacities on chest CT yes/no) based on the radiological attending report
- Medical Comorbidities and secondary diagnoses
- Use of supplemental oxygen (yes/no)

Study specific

- If not included in SOC, documentation of negative urine pregnancy testing for human chorionic gonadotropin (HCG) if female and of childbearing potential.

Study assessments

The following study data will be documented using standard hospitalization care procedures. Research staff will collect study data from EHR (including process reports) every 24 hours during the study procedure and once a week thereafter.

8.1.1 Venous Blood Collection Timeline

Septic patients exhibit subnormal plasma ascorbate levels. Phase I studies performed at Virginia Commonwealth University (VCU) show mean ascorbate levels of 17.5 μ M (normal human ascorbate levels 60 to 70 μ M), while some other centers report undetectable plasma vitamin C in COVID-19 patients. **Baseline ascorbate levels will be drawn, before the initiation of any infusion with subsequent trough levels for PK monitoring.**

The target plasma range for modifying pro-inflammatory biomarkers and for attenuating vascular injury was obtained from the phase I safety trial and is greater than 500 μ M as measured 24 hours after initiation of Vitamin C infusion. The day 2 – 7 plasma ascorbate levels are expected to be between 500 to 1000 μ M based on prior pharmacokinetic studies generated during the phase I trial (VCU trial was entitled: Vitamin C Infusion in Human Sepsis).

Blood drawn for ascorbate levels and biomarkers will occur at hour 0 (prior to the first infusion), **hour 48 (+ or – 3 hours as long as it is drawn prior to Infusion 9), hour 96 (+ or – 3 hours as long as it is drawn at least 3 hours post Infusion 16), and hour 168 (+ or – 6 hours).**

Schedule

	Baseline (hour 0)	Treatment days 1-4 (hour 24)	Treatment days 4-7	Days 7-14	Days 14-21	Phase 1 Study end (day 28)	Phase 2 Day 60 and Day 90
Death from ANY cause	X	X	X	X	X	X	X
Alive and Free of any	X	X	X	X	X	X	

respiratory failure							
Alive and free from invasive mechanical ventilation	X	X	X	X	X	X	
AKI (y/n) and stage	X	X	X	X	X	X	
WHO COVID-19 SCALE	X	X	X	X	X	X	X
Concomitant medication use(a)	X	X	X	X	X	X	
Plasma levels (b)	X	X	X	X	X	X	
Vital signs (c)	X	X	X	X	X	X	
Clinical assessment for kidney stone symptoms	X	X	X	X	X	X	
qSOFA score	X	X	X	X	X	X	
Ins/Outs	X	X	X	X	X	X	
Ventilator status / oxygen (e)	X	X	X	X	X	X	
Ventilator-free days	X	X	X	X	X	X	
AKI-free days	X	X	X	X	X	X	
24-hour urine collection			X5, X7	X14*	X21*	X28*	
Ventilator and drip data	X	X	X	X	X	X	
AE/tolerance (g)		X	X				
Mortality (h)	X	X	X	X	X	Date/time	
Discharge (i)	X	X	X	X	X	Date/time	
WHO COVID-19 Scale	X	X	X	X	X	X	

Footnotes:

- a. Concomitant medication use (if applicable): oxygen therapy (to calculate S/F ratio), oxygen device, antibiotics, COVID-19-specific (remdesivir, dexamethasone, tocilizumab, sarilumab, canakinumab, hydroxychloroquine, azithromycin, convalescent plasma, remdesivir) corticosteroids, albumin, thiamine, norepinephrine, vasopressin, and N-acetylcysteine, antiplatelet and anticoagulants, muscle relaxants, sedatives (propofol, midazolam) and opioid analgesia.
- b. Plasma levels: serum oxalate, creatinine, hematology, coagulation, biomarkers (ferritin, C - reactive protein (CRP), lymphocyte count, LDH, d-dimer). If the primary team does not obtain these tests, we will obtain them for study purposes (dedicated blood draw if needed on day 0 and 7) and as add-on-labs (no study-specific blood draw on days 1-4).
- c. Vital signs: Temperature, Respiratory Rate, Systolic and Diastolic Blood Pressures, Heart Rate, RASS score, Alert/ Not Alert, Oriented/ Not Oriented, FiO₂, oxygen delivery device.
- d. Ins/Outs: 24-hour oral or IV intake/output and dialysis/ CRRT details at midnight.
- e. Current ventilation status: use of mechanical ventilator or oxygen device (yes/no), mode, invasive/ non-invasive ventilation, FiO₂, PEEP, Plateau Pressure
- f. Ventilator/CCRT/Vasopressor/Delirium: last 7 days
- g. Adverse Events and tolerance: Interview with patient, may be conducted by telephone if feasible to reduce exposure of study personnel
- h. Mortality: date-time of death and all-cause mortality and likely cause of death.
- i. Discharge: Discharge date-time and discharge disposition (home, rehabilitation, skilled nursing facility, hospice, transfer to other hospital)
- j. For respiratory failure: was the patient at any time: turned to the prone position to facilitate oxygenation, paralyzed, placed on ECMO, had a tracheostomy placed?

Phase 1 End

- Total ventilator free days, CRRT free days, Vasopressor free days, and Delirium free days.
- Is patient still hospitalized?
- For respiratory failure, was the patient at any time: turned to the prone position to facilitate oxygenation, paralyzed, placed on ECMO, had a tracheostomy placed?
- Is patient still alive? If not, date/time and cause of death and code status at time of death.

Phase 2 follow-up (>=90 days)

- Is patient still alive? If not, date/time and cause of death and code status at time of death.

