	Limitation of Activities	2
Hospitalized mild disease	Hospitalized, no oxygen therapy	3
	Oxygen by mask or nasal prongs	4
Hospitalized Severe Disease	Non-invasive ventilation or high-flow oxygen	5
	Intubation and mechanical ventilation	6
	Ventilation + additional organ support – vasopressors, renal replacement therapy, ECMO	7
Dead	Death	8

Secondary Endpoint A (Safety): Daily renal safety biomarkers on the day of randomization (Day 0), then day 1-7. These include (1) daily serum oxalate levels, (2) daily urine microscopic analysis for the presence of oxalate stones (3) daily random urine oxalate and 24-hour urine oxalate levels on days 5,7 and 14.

Secondary Endpoint B (Safety): acute kidney injury-free days at day 28, 90 (stemming from daily AKI assessment while patient is in the hospital).

Secondary Endpoint C (Safety): All-cause mortality to day 28, 60 90 (daily assessment).

Secondary Endpoint D: (Exploratory): COVID-19 and sepsis-specific inflammatory marker levels on Day 0, then on day 7. These include (1) ferritin, (2) D-dimer, (3) lactate dehydrogenase (LDH), (4) interleukin-6, and (5) Trough ascorbate plasma concentrations at 24 hours, 48 hours, 96 hours and final plasma concentration assessment at 168 hours.

Secondary Endpoint E: (Safety): Proportion of patients alive and free of respiratory failure through 28-days. (Respiratory failure defined as resource utilization requiring at least 1 of the following: Endotracheal intubation and mechanical ventilation, Oxygen delivered by high-flow nasal cannula (heated, humidified, oxygen delivered via reinforced nasal cannula

at flow rates >20L/min with fraction of delivered oxygen ≥ 0.5), noninvasive positive pressure ventilation, extracorporeal membrane oxygenation).

Secondary Endpoint F: (Safety): Proportion of patients alive and free of invasive mechanical ventilation at 28-days.

CLINICAL STUDY PROTOCOL

C. Kenneth and Dianne Wright
Center for Clinical and Translational Research

Study Population

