	including lymphocyte ratio, including potassium, magnesium and phosphorus, LDH, D-Dimer, CRP, Ferritin, ABG, Urinalysis all if performed for patient care, pregnancy test (if applies and was not obtained)									
	Bilirubin Total, AST, ALT, ALP, albumin	R				R7	S	S	S	
	Received Steroids last 24 hours or last week? Steroid type and daily cumulative dose [for daily assessment]	S	S	S	S	S	S	S	S	
	COVID-19 specific treatments, anticoagulants, and dosage: Remdesivir Dexamethasone Anticoagulants Other COVID-19 treatments	S	S	S	S	S	S	S	S	
	Any atrial arrhythmias over the last interval [afib, aflutter, SVT]	S	S	S	S	S	S	S	S	
	12-Lead EKG	R	S	S	S	S	S	S	S	S
	Any significant ventricular arrhythmias over the last interval [not PVCs]	S	S	S	S	S	S	S	S	
	Chest X-Ray Chest Computer Tomography	S	S	S	S	S	S	S	S	S
	24-hour urine oxalate on day 5 (after completion of the last dose)	S	S	S	S	R	S	S	S	S
	Lowest daily blood glucose Highest lactate dehydrogenase	RS	R	R	R	RS				

	(LDH), serum									
	Highest D-dimer, plasma									
	Highest ferritin, plasma									
	Highest C-reactive protein (CRP), plasma									
	IL-6, plasma									
	Baseline and Trough Ascorbic Acid (vitamin C levels)	R	R	R	R	R7				
	AKI free-days days	S	S	RS	S	S	S	S	S	
	Urinalysis evaluation for stones									
	Is the patient still hospitalized? If not Discharge date time								R	
	Total Ventilator-Free Days								R	
	Was the patient paralyzed for ARDS at any point?								R	
	Was placed on iNO at any point?								R	
	Was placed in a prone position at any point?								R	
	Was placed on ECMO at any point during this hospitalization? [VA or VV]								R	
	Did the patient had a tracheostomy at any point in this hospitalization?								R	R
	Date and Time of Death if applies								R	R
	Cause of Death if applies								R	R
	DNR? If yes when was DNR first placed								R	R
	Phone clinic follow-up patient-reported outcome measure									R

PROMIS Dyspnea Assistive Devices and Resources score (version 1.0).								
Footnotes								
The study protocol does not include phlebotomy (new stick) just for study labs for days 1-4. If labs are obtained for any other reason, then study labs marked as “R” will be collected as “add-on” to the hospital lab. The protocol does include study labs that will be used specifically for Research marked as RS.								

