6.1.1 Dosing and Administration

- First study drug dose (L-ascorbic acid, 50 mg/kg infusion over 30 minutes) will be considered "Dose 1" and will be administered within the first 8 hours of enrollment or

the earliest available time post any clinically indicated procedure which requires the patient to be off the unit. Doses will be administered in the ED, medicine inpatient unit or ICU. Patients receiving vitamin C will receive 25% of the total daily calculated dosing (200 mg/kg/24 hours) infused over 30 minutes every 6 hours for 96 hours.

- Subsequent doses will be **50 mg/kg infused over 30 minutes every 6 hours.**
 - Timing of Dose 2 will be triggered by the physician order for every 6-hour administration and will, therefore, be listed on the bedside medical administration record (MAR). As such, the timing of Dose 2 may be out of the +/- 3-hour window and will not trigger a protocol deviation.
 - If for any reason any other maintenance dose is not administered within the window, the dose will be skipped, and the next scheduled dose will be given and documented in the data collection tool.

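### The hour-48 and hour-96 ascorbate windows in 8.1.1 do not ensure trough samples, and some permitted Dose 2 times leave no valid draw time

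*Combined protocol and SAP*

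**What the plan says.** - **Endpoint.** Secondary Endpoint D in the Synopsis, labelled exploratory, includes "Trough ascorbate plasma concentrations at 24 hours, 48 hours, 96 hours and final plasma concentration assessment at 168 hours". Section 3.1 lists the same times and justifies them by the lack of pharmacokinetic knowledge in this population.
- **Sampling.** Section 8.1.1 has the baseline sample drawn "before the initiation of any infusion with subsequent trough levels for PK monitoring". The later draws are set at "hour 48 (+ or – 3 hours as long as it is drawn prior to Infusion 9", at "hour 96 (+ or – 3 hours as long as it is drawn at least 3 hours post Infusion 16", and at hour 168. That sentence gives no hour-24 draw. The same section defines its target (above 500 µM) at 24 hours after the start of treatment and expects 500 to 1000 µM on days 2 to 7.
- **Dosing.** In 6.1.1 the daily dose is split into quarters "infused over 30 minutes every 6 hours for 96 hours"; 4.1 counts sixteen infusions. Dose 2 follows the physician's order: "As such, the timing of Dose 2 may be out of the +/- 3-hour window and will not trigger a protocol deviation". No outer bound is given. Any other dose outside its window is skipped, and nothing says how infusions are numbered afterwards.
- **How the tube is obtained.** The Schedule of Activities codes ascorbate on the treatment days as R, an add-on to hospital blood work. Its footnote states: "The study protocol does not include phlebotomy (new stick) just for study labs for days 1-4".

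**The concern.** A trough is the level just before the next dose. With dosing every 6 hours, a tolerance of 3 hours on either side of a clock time spans a whole dosing interval. Whether a given sample is a trough then depends on when the draw happens and on how far that patient's infusions have moved from the clock. The hour-96 rule guards against early draws with a minimum of 3 hours after the infusion. The hour-48 rule, in the same sentence, has no such minimum.

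At stake is the interpretation of the ascorbate data. If time since infusion varies between patients and is not recorded against the sample, a high value may reflect an early draw and not slower clearance. The text of Section 9 describes no pharmacokinetic analysis and no adjustment for time since infusion that would separate the two.

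**Working it through.** **Inputs.** Infusions last 0.5 h and are given every 6 h for 96 h (6.1.1). Sampling windows are those in 8.1.1. Hour 0 is taken as the first infusion, as 8.1.1 implies. Later doses are assumed to follow Dose 2 at 6-hour steps.

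**The plan's own count.** 96 / 6 = 16 infusions, which agrees with 4.1.

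**Nominal schedule.** Infusion k starts at hour 6(k − 1).
- Infusion 8: hours 42 to 42.5. Infusion 9 starts at hour 48. Infusion 16: hours 90 to 90.5.
- Hour-48 window: from 48 − 3 = 45 up to Infusion 9 at 48. Time since the end of Infusion 8: 45 − 42.5 = 2.5 h to 48 − 42.5 = 5.5 h.
- Hour-96 window: from the later of 93 and 90.5 + 3 = 93.5, up to 99. Time since the end of Infusion 16: 3.0 to 8.5 h. If the 3 hours count from the infusion's start, the window opens at 93, or 2.5 h after its end.

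**Dose 2 at d hours after Dose 1.** Infusion 8 starts at d + 36, Infusion 9 at d + 42 and Infusion 16 at d + 84.
- The hour-48 window is empty if d + 42 ≤ 45, so d ≤ 3.
- At d = 4 it is hours 45 to 46.
- At d = 8, Infusion 8 ends at 44.5, so a draw at hour 45 qualifies 0.5 h after it ends.
- At d = 9, Infusion 8 starts at hour 45. From there it falls inside the window, and a sample at its end qualifies.
- The hour-96 window is empty if d + 84 + 0.5 + 3 > 99, so d > 11.5 (d > 12 if counted from the infusion's start).

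The values d = 3 and d = 8 lie within the ±3 h window around a 6-hour Dose 2, so these two cases do not need the exemption in 6.1.1. If the same ±3 h applies to later doses, Infusion 9 given 3 h early (hour 45) also empties the hour-48 window.

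**If hour 0 meant enrollment.** Dose 1 may come up to 8 h after enrollment (6.1.1). With a delay of D1, the hour-96 window is empty if D1 + 90.5 + 3 > 99, so D1 > 5.5 h. The End of Study Definition in the Synopsis counts 96 hours from randomization, so the origin needs stating.

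**Size of a timing error.** The documents give no half-life. Assume mono-exponential decline with half-life 2, 4 or 8 h and ignore the endogenous level. A draw 3 h early reads 2^(3 / half-life) times the trough:

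| Assumed half-life | Ratio | A true 500 µM trough reads about |
|---|---|---|
| 2 h | 2.83 | 1,410 µM |
| 4 h | 1.68 | 840 µM |
| 8 h | 1.30 | 650 µM |

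The expected band is 1000 / 500 = 2-fold wide.

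**The case against.** A reader might infer that the samples are simply not troughs. The documents do not support that. On schedule, a draw just before Infusion 9, or at hour 96, falls 5.5 h after the preceding infusion ends, which is trough time. Section 8.1.1 also ties both samples to an infusion and calls them troughs. The windows permit non-troughs; they do not impose them.

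A reader might also infer that some patients will have no valid hour-48 time. That is conditional on an early Dose 2 or an early Infusion 9, and 6.1.1 gives neither direction nor frequency.

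Nor do the hour-48 and hour-96 windows undermine the 500 µM target, because it is defined at hour 24. The 500 to 1000 µM band is an expectation, not a decision rule. The plan specifies no comparison of hour 48 with hour 96 and none of ascorbate by kidney injury, so losses there cannot be charged to it. The contrast with untreated levels is safe: 8.1.1 cites a septic mean of 17.5 µM, and 500 / 17.5 is about 29-fold, far beyond a 1.3- to 2.8-fold timing error.

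Finally, infusions appear on the medication record and in drug logs (6.1.1, 6.4), so their times may be recoverable, and 2.3.1 allows draws through existing lines. These points limit the impact. What remains is that the stated rule admits draws from near peak to well past trough, can have no solution, and does not say that time since infusion will be recorded or used.

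**Conclusion.** The concern holds in a limited form: the clock windows in 8.1.1 do not ensure troughs. The nominal range is 2.5 to 5.5 h after Infusion 8 and about 3.0 to 8.5 h after Infusion 16. It widens, or a window closes, when Dose 2 moves.

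The window arithmetic rests on hour 0 being the first infusion and on 6-hourly dosing after Dose 2. The fold-errors rest on assumed half-lives: at 2 h a 3-hour error exceeds the width of the expected band, while at 4 and 8 h it does not. The frequency of empty or near-peak windows is unknown.

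The effect is confined to exploratory Secondary Endpoint D. The primary outcome is untouched. The change is worth making because it is cheap and the ascorbate levels are collected for their pharmacokinetic content.

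**What to change.** Amend 8.1.1 as follows; no dosing rule changes.

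1. Define hour 0 as the start of the first infusion.
2. Draw the hour-48 sample within 60 min before the actual start of the infusion due at hour 48, and at least about 4.5 h after the end of the preceding infusion given. On schedule this is hours 47 to 48.
3. Draw the hour-96 sample 6 h (±60 min) after the start of the last infusion given. On schedule this is hours 95 to 97.
4. Add a matching rule for the hour-24 trough, which Secondary Endpoint D lists and on which the 500 µM target is defined.
5. State how infusions are numbered after a skipped dose.
6. Record the start and stop of the preceding infusion and the draw time. Report off-window samples separately with their time since infusion; do not discard them.
7. Take the tube with a hospital or laboratory-glucose draw, or through an existing line, in that window, so that the no-new-stick rule for days 1 to 4 still holds.

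Under the same assumed half-lives, a draw 1 h early reads 2^(1/2) = 1.41, 2^(1/4) = 1.19 or 2^(1/8) = 1.09 times the trough.

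The cost is amendment wording, a nursing instruction and a few missed or off-window samples. If the preceding infusion ran late, the 4.5 h minimum may not be reachable before the next one; that sample is then reported as off-window. Laboratory-glucose draws follow the clinicians' schedule, so some will not fall in the window.

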8.2 Safety and Other Assessments

The following data will provide the basis for assessing protocol compliance and safety as well as between-group differences in several efficacy variables. Data for each of the variables will be recorded on the days shown in the time-events schedule table. This trial will use the Common Terminology Criteria for Adverse Events version 5 (CTCAE v. 5) to assess safety and severity of symptoms.

8.2.1 Every 24 hours for as long as the patient is in the hospital: input/output, hypoglycemic events, creatinine, worst vital signs, and oxygen requirement, dialysis, admission to the ICU or need for mechanical ventilation. COVID-19 WHO ordinal status, daily serum chemistries, CBC, magnesium, telemetry ECG tracing monitoring and continuous oximetry monitoring. Patients are monitored for gastrointestinal tolerability (i.e., nausea, diarrhea) and for other adverse events (i.e., rash, headache) and agent will be **stopped** for CTCAE V5 for grade 3 or higher, while the study monitoring will continue.

8.2.2 Every, 24, 48, hours: Acute Kidney Injury-free days, Worst vital signs, Serum electrolytes, chemistries, concurrent medications AE/SAE Assessments, Weight, Bilirubin, Oxygenation Data, Kidney stone symptoms

8.2.3 Every 7, 14, 21 and 28 days: Required: Ventilator Free Days to Day 28, All-Cause Mortality to Day 28, oxygenation indices, oxygen device, use of dialysis. COVID-19 WHO ordinal status.

8.2.4 Sixty and 90 Days: All-cause mortality, routine evaluations of organ function, functional status

8.2.5 All patients will be treated **at minimum** subcutaneous unfractionated heparin for thrombo-prophylaxis (5000 units TID). Anticoagulation may be escalated by the treating physicians based on clinical and laboratory variables, such as the D-Dimer and the thromboelastogram (TEG). If suspicion of clotting arises immediate thromboelastography (TEG) will be performed to determine if clotting is ongoing. If TEG supports clotting suspicions doppler ultrasound **of the appropriate venous site** will be performed.

8.2.6 Assessment of hepatic safety: Hepatic transaminases will be monitored at baseline, day 2 and day 3 or the study. Persistent elevations will lead to: 1) discussion with ward staff, 2) will lead to right upper quadrant ultrasonography, and 3) Consultation from the Hepatology service.

8.3 Adverse Events and Serious Adverse Events

8.3.1 Definition of Adverse Events (AE)

Adverse event means any untoward medical occurrence associated with the use of an intervention in humans, whether or not considered intervention-related (21 CFR 312.32 (a)

8.3.2 Definition of Serious Adverse Events (SAE)

An adverse event (AE) or suspected adverse reaction is considered "serious" if, in the view of the investigator, it results in any of the following outcomes: death, a life-threatening adverse event, inpatient hospitalization or prolongation of existing hospitalization, a persistent or significant incapacity or substantial disruption of the ability to conduct normal life functions, or a congenital anomaly/birth defect. Important medical events that may not result in death, be life-threatening, or require hospitalization may be considered serious when, based upon appropriate medical judgment, they may jeopardize the participant and may require medical or surgical intervention to prevent one of the outcomes listed in this definition.

